3.2.3 Study Timeline Summary

Screening	Baseline and Surgery	Post Treatment Evaluation				
Visit 1	Visit 2	Visit 3	Visit 4	Visit 5	Visit 6	Visit 7
Within 32 days of surgery	Day 0	Week 1 ± 3 days	Month 1 ± 7 days	Month 3 ± 14 days	Month 6 ± 14 days	Month 12 ± 14 days

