3.2.4 Safety Endpoints

Assessments of subject safety will include a tabulation of the incidence of adverse events.

All treatment-related adverse events that occur up to 30 days excepting surgery related AEs within 48 hours after any treatment will be recorded, and all serious adverse events throughout the study will be recorded.

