3.4.2 Study Treatments

Screening will take place no more than 32 days prior to the first treatment and will include the clinical assessments required to confirm eligibility. Informed Consent Form will be signed at Screening Visit (Visit 1). Clinical photograph, radiographs of the implant treated, clinical measurements will be taken and recorded (Pocked Depth, Mucosal Recession, Clinical Attachment Level).

The day of surgery will be designated as Day 0. Subjects will have peri-implant regeneration surgery.

Whenever possible implant crown will be removed and cleaned. Healing screw will be placed on the implant. Upon flap elevation and debridement of the peri implant lesion, the operator will record the type of bony defect associated to the treated implant (see Inclusion criteria 3). Titanium Implant surface will be debrided with rotating burs and brushes (PERI-SET, Sweden&Martina Inc.), and decontaminated with EDTA (PrefGel: Straumann) for 2 minutes and with the alternation of Perio-Flow Chlorhexidine mouthwash (GUM® ParoEx®, Chlorhexidine Gluconate Oral Rinse USP 0,12% SUNSTAR), saline water and H₂O₂ using cotton pellets. After the completion of these procedures, Easy-graft® CLASSIC will be placed on the peri-implant defect surface. GUIDOR® Bio-resorbable Matrix Membrane will be

placed on top of the easy-graft classic and stabilized. If the implant crown was successfully removed, flaps will be primary closed and the implant will be covered completely. Second stage, minimally invasive surgery to gain access to the implant will be performed at 6 months. Intraoperative and postoperative measurements will be made and the flap will be closed with sutures. Patients will be instructed to take 500 mg of amoxicillin three times a day for 7 days, starting at least one hour prior the procedure.

Fifteen (15) male or female subjects, aged 21 to 85 years, will be recruited for the study from existing patient databases, as well as, from screenings of volunteers responding to advertisements, if necessary.

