3.4.5 Management of Post-Surgical Oral Pain

Any pre-surgical pain medications should be recorded and noted as such (i.e. pre-surgical pain medication). Post-surgical pain can be divided into mild, moderate, and severe levels and requires a subjective assessment by the periodontists based on knowledge of the surgical procedure performed and the presenting signs and symptoms of the subject. Pain as a secondary outcome to an adverse event, such as infection, is to be excluded if pain is an expected outcome of such events. Treatment of the pain is usually the best indicator of pain intensity.

MILD (Over-the Counter)

Acetaminophen 250 or 500 mg.

Products include: Tylenol®, Datrex®, Anacin®3

Ibuprofen

Products include: Motrin® 800 mg

MODERATE (Prescription Only)

Tylenol® No. 3 (codeine and acetaminophen)

Vicodin® (hydrocodone 5 mg and acetaminophen 500 mg)

Vicodin ES® (hydrocodone 7.5 mg and acetaminophen 750 mg)

Lortab® (hydrocodone 5 mg, 7.5 mg, 10 mg and acetaminophen 500 mg)

SEVERE (Prescription Only)

- Demerol® 50 mg (Meperidine)*
- Percocet® or Tylox® (oxycodone 5 mg and acetaminophen 500 mg)*

**Triplicate prescription where applicable*

3.4.6 Post-surgical Control, Professional Tooth Cleaning , Maintenance Care.

The objective of the post-operative appointments for professional tooth cleaning is both the removal of plaque and staining from the treated areas and the monitoring of the healing events. Post-surgical controls and professional tooth cleaning will be performed at 3, 6 and 12 months post-surgical. At these appointments, the conditions of the soft tissue at the treated sites will be evaluated. The overall level of oral hygiene will be evaluated and reinstruction will be given as needed at all visits.

Instructions on post-operative care will be repeated at each appointment. In particular, the following points should be covered during the first month: (1) continue chlorhexidine rinses

(from surgery to four weeks post-op); (2) resume gentle brushing; and (3) avoid vigorous chewing on, or trauma to, the treated areas.

At week 6, subjects will be instructed to gradually resume interproximal cleaning, as well as chewing, in the treated areas. All subjects will be maintained by full mouth professional prophylaxis and calculus removal once every three months, excluding surgical sites which will be maintained supragingivally.

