After the flaps have been raised and the area debrided, characterization of the morphology and measurements of the defects are made, with the UNC 15 periodontal probe, and recorded as follows:

Alveolar Bone Level (Before and after osteoplasty if needed)

Notation of intra marrow penetration of alveolar crest

Notation of alveolar crest topography and whether osteoplasty was to be performed to refine contours.

Clinical Photographs

Clinical photographs will be taken of each tooth involved in the study before, during and after surgery, at Weeks 1, and 6 post surgery and at the 3, and 6 month follow-up examinations.

Post-Op Discomfort and Satisfaction Questionnaires

The subject's satisfaction with respect to postoperative discomfort between test and control quadrants will be evaluated by asking the subject about pain, bleeding, swelling and sensitivity using 10 cm visual analogue scale (See Appendix 1).

Procedure/ Assessment	Visit 1	Visit 2	Visit 3	Visit 4	Visit 5	Visit 6	Visit 7
	Screen 0-32 Days	Prior Surgery	Day 0	Post-op Day 7	1 Month 42± 7 Days	Month 3 90± 14 Days	Month 6 ±14 Days
Informed Consent	X						
Eligibility/ Study Lesion Identification, Subject Registration	X						
Demographics/Dental/Medical History	X						
O'Leary Plaque Index	X					X	X
Probing Depths	X					X	X
Pregnancy Test	X ¹						
Radiographic Exam	X					X	X
Dental Cleaning	X				X	X	X

CONFIDENTIAL AND PROPRIETARY INFORMATION OF Creighton University School of Dentistry Department of Periodontics

Protocol Number: CUSD2

Original Issue Date: January 6th 2017

Digital Photos		X	X	X	X	X	X
Examiner and Subject GORS and VAS of esthetic satisfaction		X	X	X	X	X	X
Plaque Control/Oral Hygiene Instruction	X	X	X	X	X	X	X
Concomitant Medications	X	X	X	X	X	X	X
Adverse Events		X	X	X	X	X	X
Clinical Attachment level	X					X	X
Examiner calibration		X					
Easy Graft Classic surgery		X					
Second stage surgery for submerged implants only						X	
Rate and record Judgment of Healing			X	X	X	X	X
Pain Rating Scale			X	X	X	X	X
Color and Texture			X	X	X	X	X
Width of Keratinized Tissue				X	X	X	X

1. In females of child-bearing potential only

CONFIDENTIAL AND PROPRIETARY INFORMATION OF Creighton University School of Dentistry Department of Periodontics

Protocol Number: CUSD2

Original Issue Date: January 6th 2017

Page 43 of 63

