4.0 ADVERSE EVENTS

Recording and Reporting Adverse Events

An Adverse Event (AE) is defined as any untoward medical occurrence in a subject of a clinical investigation administered an investigational product and that does not necessarily have a causal relationship with this treatment. An AE can therefore be any unfavorable and unintended sign (including an abnormal laboratory finding), symptom, or disease temporally

associated with the use of an investigational product, whether or not related to use of the product.

Recording Adverse Events

All adverse events occurring after surgical procedure will be collected during the entire trial.

Each adverse event will be followed until the adverse event has resolved or stabilized.

During visits, subjects should be encouraged to report adverse events spontaneously or in response to general, non-directed questioning.

- Standard medical terminology for the AE and the associated body system
- Description of adverse event and clinical consequences
- Date and time of onset
- Date and time of resolution of the adverse event
- Whether or not the event is ongoing
- Severity of the event
- Relationship between the adverse event and the investigational agent or related procedure
- Description of any therapy administered and associated outcome (actions required)
- Outcome of the AE
- Whether or not the effect was serious and/or unanticipated

All AEs, regardless of seriousness, severity, or presumed relationship to study therapy, must be recorded using medical terminology in the source document and on the adverse event case report form.

Whenever possible, a diagnosis should be given when signs and symptoms are due to common etiology (e.g., cough, runny nose, sneezing, sore throat, and head congestion should be reported as “upper respiratory infection”).

Each adverse event should be reported separately. For example, “nausea and vomiting” should be recorded as two (2) separate events.

Grading Adverse Events

Common Terminology Criteria for Adverse Events v3.0, (on the NCI website, <http://ctep.info.nih.gov>) will be used to grade all toxicities/adverse events. Adverse events not included in the CTCAE v.3.0 should be reported with common medical terminology and graded according to definitions in the CTC Manual.

Assigning Relationship of Adverse Events to Treatment

A relationship must be assigned by the investigator to each reported adverse event, and will be documented as follows:

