5.0 STATISTICAL AND ANALYTICAL PLAN

Intent to Treat Population

The primary efficacy analysis and summaries will be performed on the “intent to treat” (ITT) population, defined as all subjects who successfully completed the screening to enter this trial.

Safety Population

All safety summaries and analyses will be performed on the safety population, defined to be all subjects.

Evaluable Population

All secondary efficacy analyses will be performed on an evaluable population, defined to be all subjects who received surgical treatment in accordance with the protocol.

Subjects exiting after undergoing surgery, but before month 6 due to treatment-related adverse events will be included in the evaluable population. Subjects that do not complete the assessments due to satisfaction with treatment will also be included in the evaluable population. All attempts will be made to collect complete follow-up evaluations for these subjects despite study exit. These subjects will be included in the analysis based on the assessments that are completed.

Subjects will be deemed non-evaluable if they do not meet the eligibility criteria as outlined in the protocol. Other reasons to be considered non-evaluable include protocol violations, as described below, and any actions that compromise the effectiveness of the treatment, for non-efficacy or safety related reasons.

Protocol violators consist of subjects who do not comply with the protocol in terms of treatment administration, visit timing, and/or assessment compliance. Each protocol violation will be discussed between Investigators and the Sponsor to evaluate the impact on the statistical assessment before performing the analyses.

Missing Data

It is not anticipated that many subjects will exit the study prematurely or will miss visits. The reasons for early termination, along with the timing of the early terminations will be provided.

Subjects missing a baseline evaluation will be discussed between Investigators and the Sponsor to evaluate the impact on the statistical assessment before performing the analyses

Assessment of Safety

Adverse events with an onset within 30 days of any surgical treatment will be recorded and tabulated. All adverse events will be tabulated by first occurrence of the event, maximum severity, and strongest relationship to study treatment by body system.

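### No adverse event or pain assessment is scheduled between the month 6 second-stage surgery and month 12, so the 30-day safety window after that operation contains no scheduled assessment after the day of surgery

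*Combined protocol and SAP*

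**What the plan says.** Where the crown can be removed, the implant is submerged at the graft operation, and section 3.4.2 then provides: "Second stage, minimally invasive surgery to gain access to the implant will be performed at 6 months". The flowchart has a row for it, "Second stage surgery for submerged implants only", marked at the sixth visit.

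Section 3.2.3 places Visit 6 at "Month 6 ± 14 days" and Visit 7 at "Month 12 ± 14 days", with no visit between them. Sections 3.6.6 and 3.6.7 list adverse event collection, the pain scale and pain-medication review at those two visits.

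The safety analysis in section 5.0 states: "Adverse events with an onset within 30 days of any surgical treatment will be recorded and tabulated". Section 3.2.4, repeated at the end of 3.4.6, has a narrower rule: "All treatment-related adverse events that occur up to 30 days excepting surgery related AEs within 48 hours after any treatment will be recorded". Section 4.0 has a wider one: "All adverse events occurring after surgical procedure will be collected during the entire trial". It describes questioning subjects about adverse events at visits.

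Section 3.4.6 adds maintenance: "All subjects will be maintained by full mouth professional prophylaxis and calculus removal once every three months". The same section lists post-surgical controls only at 3, 6 and 12 months.

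**The concern.** The two protocol operations are not observed alike. After the graft operation, adverse events, pain, healing and pain medication are reviewed at week 1, month 1 and month 3. After the second-stage operation, nothing comparable is scheduled until month 12, although section 5.0 appears to apply the same 30-day window to both.

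Safety in this study rests on the tabulated incidence of adverse events. Appendix I treats moderate or severe sensitivity, bleeding or swelling as an adverse event to be recorded. Such events can come and go within weeks. If the first enquiry comes months after the window has closed, some will not be recalled, or will be recalled without a usable onset date. An event nobody has heard about also cannot be followed to resolution, as section 4.0 requires.

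**Working it through.** The plan gives no figure to reproduce, so this is calendar arithmetic on the visit schedule.

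**Inputs**
- Second-stage surgery: month 6, window ±14 days (3.4.2, 3.2.3). Assumed to take place on the Visit 6 date.
- Next scheduled assessment: month 12, window ±14 days (3.2.3).
- Adverse event window: 30 days after any surgical treatment (5.0).
- Visits after the graft operation: week 1 ±3 days and month 1 ±7 days (3.2.3). The flowchart gives 42 ±7 days for the 1-month visit.
- Maintenance: every three months (3.4.6).

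**Gap after the window closes** = Visit 7 − (Visit 6 + 30 days)

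With 30-day months, as section 3.6.5 uses for month 3 (day 90):
- Visit 6: 180 ± 14 = day 166 to 194. Window closes: day 196 to 224.
- Visit 7: 360 ± 14 = day 346 to 374.
- Nominal gap: 360 − 210 = 150 days. Shortest: 346 − 224 = 122. Longest: 374 − 196 = 178.

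With calendar months (365.25 / 12 = 30.44 days):
- Visit 6 to Visit 7: 182.6 days. Nominal gap: 182.6 − 30 = 152.6 days.
- Shortest: 152.6 − 28 = 124.6. Longest: 152.6 + 28 = 180.6.

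Both conventions give about five months, with an overall range of about 122 to 181 days.

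**Month 9 prophylaxis**
- Three months after Visit 6 is 90 to 91 days, which is 60 to 61 days after the window closes.

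**Scheduled assessments inside each 30-day window, after the day of surgery**
- Graft operation: week 1 (days 4 to 10) is clearly inside. Month 1 (about days 23 to 37) may be inside. On the flowchart timing (days 35 to 49) it is outside.
- Second-stage operation: none.

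**Can Visit 6 fill the gap?** No. Its adverse event and pain items fall on the day of the operation at the latest. Section 3.6.6 does not say whether they come before or after the procedure.

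**Can the month 12 pain scale fill it?** No. The Appendix I scale asks for the patient's level of pain and gives no recall period, so it reads as current pain.

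**Labels.** The flowchart's day headings, as extracted, are out of step with its visit numbers, so Visit 6 is taken as month 6 from 3.2.3 and 3.6.6. Section 3.6.7 describes Visit 7 as 6 months after surgery. The 12 months of its heading and of 3.2.3 is used here.

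**The case against.** Several points on the other side limit what can be claimed.

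- **Contact before month 12.** A reader might infer that submerged subjects are not seen at all between months 6 and 12. Section 3.4.6 does not support that: three-monthly prophylaxis implies a contact near month 9. It falls outside the 30-day window, however, and has no adverse event or pain item attached.
- **Recall as the only route.** A reader might also infer that every event would depend on memory at month 12. Serious events must be reported within one day of awareness, and section 4.0 collects all events throughout the trial and follows each one. This stands for serious events. For non-serious ones, no route between visits is described.
- **A flattering subgroup result.** It is tempting to say that submerged subjects would look safer because nobody looked. Section 5.0 plans no comparison by submergence, and both groups have the same visit schedule. What remains is incomplete counting of events from an additional procedure.
- **The second window is a reading.** Elsewhere, surgical treatment usually means the graft operation, and the word any could refer to several implants in one subject. The text does not settle this, but on its plain wording a protocol operation listed under study treatments is included.
- **Other rules shrink the effect.** Section 3.2.4 restricts recording to treatment-related events and excepts surgery-related ones within 48 hours. Section 5.0 tabulates first occurrences, so an event type already seen after the graft may not change the table. The first conflicts with section 4.0. The second is a reason to tabulate by operation.
- **Partial retrospective data.** The discomfort questionnaire has a duration field, and pain medication is reviewed at month 12. These may recover something, but not reliably.
- **Purpose.** The documents do not say that pain after the second stage is meant to be measured, and they call that procedure minimally invasive. This lowers the weight of the pain item without removing the safety gap.

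**Conclusion.** The point holds in a limited form. Followed as written, the schedule contains no adverse event or pain assessment in the 30 days after second-stage surgery, beyond the day itself. The next scheduled one comes nominally 150 to 153 days after that window closes (range about 122 to 181). Non-serious local events after this operation are likely to be under-counted, and post-operative pain after it would be missed rather than recalled.

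This rests on three assumptions: that any surgical treatment includes the second stage, that the operation takes place at Visit 6, and that Visit 7 is at month 12. The effect on the adverse event count cannot be sized, because the documents do not say how many implants will be submerged. Counted by subject, the ceiling is 15. The probing, attachment and radiographic endpoints are not affected by this point. It should be corrected because the remedy is cheap and the safety assessment consists of adverse event incidence alone.

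**What to change.** 1. In 3.2.3, 3.6 and the flowchart, add for subjects with submerged implants a brief contact at about 1 week and another at about 30 days after second-stage surgery. Record adverse events, pain medication and a verbal pain rating. The Appendix I scale is completed by drawing a line, so it cannot be used by telephone.
2. Add an adverse event review to the three-monthly prophylaxis already in 3.4.6.
3. State in 3.6.6 whether the Visit 6 adverse event and pain items are recorded before the second-stage procedure.
4. In 5.0, tabulate adverse events by operation (graft, second stage), and say explicitly that any surgical treatment includes the second stage.
5. Reconcile the three recording rules in 3.2.4 (repeated in 3.4.6), 4.0 and 5.0, and the timing of Visit 7 in 3.6.7 with 3.2.3.

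**Cost.** At most about 15 × 2 = 30 short contacts by existing staff, if each affected subject has one second-stage date, plus a case report form page and a protocol amendment. The adverse event count may rise slightly. The change concerns data collection only and leaves treatment as it is.

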3.6.4 Post op – 1 Month (Visit 4)

- Rate and record the color and texture of treated areas
- Digital photographs
- Rate and record judgment of healing
- Clinical attachment level
- The examiner and subject esthetic satisfaction VAS assessments (before and after viewing baseline photos)
- Supragingival plaque control as indicated
- Oral hygiene instruction
- Complete pain rating scale
- Concomitant medications

- Collection of Adverse Events
- Pain medication review

3.6.5 3-Months Follow up (Visit 5)

At the month 3 visit (Day 90 ± 14 days) the following procedures and assessments will be performed:

- Rate and record the color and texture of treated areas
- Digital photographs
- Rate and record judgment of healing
- Measurement of width of keratinized tissue
- Clinical attachment level
- The examiner and subject esthetic satisfaction VAS assessments (before and after viewing baseline photos)
- Supragingival plaque control as indicated
- Oral hygiene instruction
- Complete pain rating scale
- Concomitant medications
- Collection of Adverse Events
- Pain medication review
- Implant area professional cleaning

3.6.6 6 Months Follow up. (Visit 6)

Subjects will return to the clinic for a study visit 6 months (\pm 14 days) after surgery. The following procedures and assessments will be performed at this visit:

- Digital photographs
- Radiographs of all treated sites
- The examiner and subject esthetic satisfaction VAS assessments (before and after viewing baseline photos)
- Rate and record the color and texture of treated areas
- Rate and record judgment of healing
- Measurement of width of keratinized tissue
- Clinical attachment level
- Supragingival plaque control as indicated
- Oral hygiene instruction
- Complete pain rating scale
- Concomitant medications
- Probing depth
- Collection of Adverse Events
- Pain medication review
- Adverse Events review
- Implant area professional cleaning

3.6.7 12 Months Follow up. (Visit 7)

Subjects will return to the clinic for a study visit 6 months (\pm 14 days) after surgery. The following procedures and assessments will be performed at this visit:

- Digital photographs
- Radiographs of all treated sites
- The examiner and subject esthetic satisfaction VAS assessments (before and after viewing baseline photos)
- Rate and record the color and texture of treated areas
- Rate and record judgment of healing
- Measurement of width of keratinized tissue
- Clinical attachment level

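### For submerged implants, second-stage surgery and the 6-month probing measurements fall at the same visit, with no stated order or healing interval

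*Combined protocol and SAP*

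**What the plan says.** Section 3.4.2 makes crown removal the default: "Whenever possible implant crown will be removed and cleaned". Where it succeeds, "flaps will be primary closed and the implant will be covered completely", and access is regained later: "Second stage, minimally invasive surgery to gain access to the implant will be performed at 6 months".

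The flowchart in 3.7 (Summary of Clinical Assessments) has a row "Second stage surgery for submerged implants only" with a single mark, at Visit 6. The rows "Probing Depths" and "Clinical Attachment level" are each marked at Visits 1, 6 and 7. Keratinized tissue width is also marked at Visit 6. The visit list in 3.6.6 (Visit 6) includes PD, CAL and keratinized tissue width but leaves out second-stage surgery. Section 3.2.3 gives Visit 6 a window of 14 days either side of month 6, and the next study visit is month 12.

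Changes from baseline in PD, CAL and keratinized tissue width are primary endpoints in 3.2.1, and the synopsis places them at 6 and 12 months. Section 2.0 adds recession to the primary efficacy parameters.

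**The concern.** An implant that stays under the flap until month 6 cannot be probed until it is uncovered. If it is probed straight afterwards, the soft-tissue margin has just been made by the surgeon. A non-submerged implant at the same visit has a margin that has healed for about 6 months. One column of 6-month data could therefore hold two kinds of reading, plus gaps, with nothing to tell them apart. The study is a case series with no control arm (3.1), so change over time is the result and no comparison group would cancel a measurement artefact. With no rule, the two operating periodontists and the examiner could reasonably handle the same situation differently.

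**Working it through.** The plan gives no figure to reproduce here. The check compares the schedule with the measurement definitions.

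**Step 1: do the events coincide?** Flowchart rows, read by column:

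| Row | Visits marked |
|---|---|
| Second-stage surgery | 6 |
| PD | 1, 6, 7 |
| CAL | 1, 6, 7 |
| Keratinized tissue width | 4, 5, 6, 7 |

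All four share Visit 6. Sections 3.2.3, 3.4.2 and 3.6.6 independently put Visit 6 and the surgery at month 6.

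**Step 2: how far apart could they be?** Taking 6 months as 180 days, the window runs from 180 − 14 = day 166 to 180 + 14 = day 194. Surgery on the first day and probing on the last would give 194 − 166 = 28 days. Nothing in the plan asks for such a split. A non-submerged implant is read 166 to 194 days after grafting.

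**Step 3: what can be read?** Definitions are from 2.0, and from 3.7 for keratinized tissue width.

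| Measure | Starts from | Before uncovering | After uncovering, same visit |
|---|---|---|---|
| PD | Mucosal margin | No margin or pocket to read | Fresh surgical edge |
| Recession | Distance from platform to mucosal margin | No margin | Fresh surgical edge |
| Keratinized tissue width | Free gingival margin | No margin at the implant | Fresh surgical edge |
| CAL | Implant platform | Unobtainable | Platform is fixed; bias less clear |
| Radiographic bone level (3.7.5) | Implant platform on the image | Readable | Readable |

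The before-uncovering and after-uncovering entries are clinical inferences from the definitions and from the statement that the implant is fully covered.

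**Step 4: how many implants?** Call the number of submerged implants s. The documents give only a maximum of 20 implants, so s lies between 0 and 20. If submerged implants have no usable 6-month reading, n = 20 − s remain. The 95% confidence half-width of a mean change, in SD units, is t(0.975, n − 1)/√n:

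- s = 0, n = 20: 0.47
- s = 5, n = 15: 0.55
- s = 10, n = 10: 0.72
- s = 15, n = 5: 1.24
- s = 20: no 6-month reading at all

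These values of s are illustrations. The formula treats implants as independent, although up to 20 implants come from 15 subjects. The figures show loss of precision only. They do not estimate bias, because the documents give no basis for the difference between a same-day and a healed reading.

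**The case against.** The strongest reply is that a reader could take this too far.

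- **CAL.** It is tempting to say that CAL is spoiled in the same way as PD. The definitions do not support that. CAL runs from the platform, so a new margin does not move its starting point. A disturbed pocket base is possible, but the documents do not establish it. What stands for CAL is that it cannot be read before uncovering and that no order is given.
- **The analysis.** A reader might infer that the 6-month values will be pooled, or that a 6-to-12-month stability contrast will be distorted. Section 5.0 names no estimator or pooling rule. The endpoints are changes from baseline, and stability is the synopsis's heading over them. The defect lies in the schedule. Its effect depends on an analysis not yet described.
- **Size.** Converting this into millimetres of bias would need both s and a reading difference, and the plan gives neither. The procedure is described as minimally invasive, so the difference could be small.
- **Existing text.** The sentence after the second-stage surgery sentence in 3.4.2 mentions measurements during and after the operation. The same wording describes Day 0 in 3.1, and in either place it sets no order or interval.
- **Flowchart labels.** The time labels look shifted against the visit numbers, which may be an effect of text extraction. The marks share a column however the labels are read.

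The replies limit the scope and rule out a numerical bias. They do not supply the missing order or interval.

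**Conclusion.** The point holds for the 6-month readings of submerged implants. Followed as written, the schedule gives either no 6-month PD or a PD from a margin just created by surgery. The same applies to recession and keratinized tissue width. The case for CAL is weaker: unobtainable before uncovering, and not shown to be biased after it.

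The affected share is anywhere from none to all of at most 20 implants. Crown removal is attempted whenever it can be done, which suggests the share is not negligible, but no number is given and the size of any bias is unknown. It would be wrong to conclude that the trial's results as a whole are compromised. PD and CAL at month 12 are read about 6 months after uncovering, and the radiographic measures at both visits do not depend on a soft-tissue margin. The schedule should be corrected, but this is not a fatal flaw.

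**What to change.** 1. List second-stage surgery in 3.6.6 and state whether probing comes before or after it.
2. Record each implant as submerged or non-submerged on the case report form.
3. At month 6, record PD, recession and keratinized tissue width of submerged implants as not measurable. If any reading is taken on the day of uncovering, including CAL, flag it and do not pool it with healed readings.
4. Report 6-month PD, CAL and keratinized tissue width by submergence status.
5. Use month 12 as the time point at which all implants are combined for these measures.

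The cost is a few text edits and one case report form field. The price in data is fewer 6-month readings, with the loss of precision shown above for illustrative values of s. The non-submerged implants that remain at 6 months are those whose crown could not be removed, so they are a selected group. The report should say so and should not present their 6-month result as that of all treated implants.
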